## 6 Statistical methods for Pharmacodynamic (PD) parameters

### 6.1 Primary objective

The primary aim of the study is to evaluate the effect of DFV890 in addition to SoC compared with SoC alone on the APACHE II score.

#### 6.1.1 Variable

The primary clinical question of interest is: What is the effect of DFV890 in addition to SoC versus SoC alone in SARS-CoV-2 infected patients with COVID-19 pneumonia and impaired respiratory function on APACHE II severity of disease score taking into account early discharge from hospital or death but regardless of investigational treatment discontinuation?

The justification for the primary estimand is that it will capture the combined effect of investigational treatment in participants who remain in hospital for 14 days, the effect on early discharge within 14 days and the effect on death rate within 14 days, in a manner than reflects clinical practice. In this document the primary estimand will be referred to as the “**combined APACHE II score**”.

The primary estimand is described by the following attributes:

- **Population:** SARS-CoV-2 infected patients with COVID-19 pneumonia and impaired respiratory function. Further details about the population are provided in the protocol (Section 5)
- **Endpoint:** APACHE II severity of disease score on Day 15 or on day of discharge (whichever is earlier) with worst case imputation for death. Participants who die on Day 15 or earlier will be assigned the highest observed APACHE II score of any of the participants at any time during the trial. Note this imputation for death takes precedence over the APACHE II score on day of discharge.
- **Treatment of interest:** the randomized treatment (the investigational treatment DFV890 in addition to SoC or control treatment of SoC alone).
- **Handling of remaining intercurrent events:** Treatment discontinuation for any reason will be ignored and thus follow a treatment policy strategy i.e. participants who discontinue treatment will be treated in the same manner as those that continue the treatment as planned.
- **Summary measure:** The difference in variable means between treatments.

APACHE II scores are on a range between 0 and 71 points, however, in practice it is rare for any patient to accumulate more than 55 points. A decrease in the APACHE II score is considered a favorable outcome.

The APACHE II scores are derived from a number of different clinical endpoints according to the scoring table as outlined in (Knaus et al., 1985) and listed in the [Appendix](#). The handling of missing data is described in [Section 6.1.6](#).

### 6.1.2 Descriptive analyses

To assess the impact of the replacement with score values at early discharge and the worst case imputation for death on the combined APACHE II score the following summary statistics will be provided:

- only for the participants with an early discharge (i.e. prior to day 15): if APACHE II score values at the early discharge visit and the actual Day 15 visit are available these will be summarized separately by visit (“early discharge”, “Day 15”).
- In addition the frequency of worst case imputation for deaths per treatment group will be provided.

Panels of individual spaghetti plots over time for APACHE II scores and their change from baseline will be provided by treatment group. The profiles of all participants in the respective treatment group will be included in these graphs as grey lines in the background and the respective individual participants profile will be plotted with darker color in the foreground. It will be indicated by a symbol when a patient was discharged or died (see data handling rules below in [Section 6.1.7](#)).

### 6.1.3 Statistical model, assumptions and hypotheses

The combined APACHE II endpoint as described in the estimand above is assumed to follow a normal distribution.

The primary endpoint will be analyzed by an analysis of covariance model including treatment group and the three stratification factors as factors and baseline APACHE II score as a covariate. The analysis will be performed on the safety analysis set. The mean differences of DFV890 in addition to SoC vs SoC alone will be reported with 90% confidence intervals (CIs). The 1-sided p-value for the overall treatment factor will be reported.

The primary objective will be achieved if the null hypothesis that DFV890 in addition to SoC is not different to SoC alone is rejected using a one side alpha of 10%.

### 6.1.4 Model checking procedures

The appropriateness of the normality assumption of the combined APACHE II score will be assessed by graphical means e.g. residual plots.

### 6.1.5 Intercurrent events

As described in the primary estimand discontinuation of study treatment for any reason will be ignored.

### 6.1.6 Missing data

Missing data for the APACHE II score will be handled as follows:

- Missing values for age at screening will be replaced by using the stratification information assigning 3 points to participants up to 65 years ( $\leq 65$  years) and 5 points to participants above 65 years.
- Missing information on acute renal failure status: use Serum Creatinine values without renal status information.
- Subscores of the Glasgow Coma Score (i.e. responses to Best Eye Response, Motor Response, Verbal Response) scored as “untestable”, “unknown” or missing will be replaced by the last available actual score. The response “untestable” is selected if the patient is unconscious (e.g. through sedation in case of mechanical ventilation).
- Missing values in any of the other parameters required for the derivation of the APACHE II score will be replaced by the last available assessment, as long as data is not carried forward by more than 4 days.

For a given visit, these missing data rules will only be applied if for at least one of the parameters contributing to the APACHE II score a value was reported for this specific visit.

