## Serum creatinine (mg/dL)

RSORRES	RSSTRESC	RSSTRESN
>=3.5 and acute renal failure ="yes"	8	8
2-3.4 and acute renal failure ="yes"	6	6
1.5-1.9 and acute renal failure="yes"	4	4
>=3.5	4	4

2-3.4	3	3
1.5-1.9	2	2
0.6-1.4	0	0
<0.6	2	2

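### A missing acute renal failure status is scored as no renal failure even when a recent positive status is on record, which halves the creatinine points for participants who have it and creatinine of at least 1.5 mg/dL

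*SAP*

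**What the plan says.** SAP section 6.1.6 sets separate missing-data rules for the inputs to the APACHE II score.

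- Acute renal failure status: "Missing information on acute renal failure status: use Serum Creatinine values without renal status information".
- Glasgow Coma subscores: those scored as untestable, unknown or "missing will be replaced by the last available actual score". No time limit is attached.
- Everything else: "Missing values in any of the other parameters required for the derivation of the APACHE II score will be replaced by the last available assessment", with a limit of 4 days. Because this rule covers only the other parameters, it does not reach renal failure status, which has its own rule.

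The section closes by limiting these rules to visits where some contributing input was entered, so the rules work visit by visit.

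The creatinine table in section 10.2.1 has three rows that need a positive renal status: ">=3.5 and acute renal failure ='yes" (8 points), "2-3.4 and acute renal failure ='yes" (6 points) and "1.5-1.9 and acute renal failure='yes" (4 points). The same three creatinine ranges without that status score 4, 3 and 2. Under section 6.1.8 the combined APACHE II score, which is the primary endpoint, is derived after these missing-data rules have been applied.

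**The concern.** Scoring creatinine without renal status information gives the same result as recording that there is no acute renal failure. That is a reasonable last resort when nothing is known. The rule, however, applies to every blank, including one where a positive status was entered at the previous visit. The creatinine value gets a 4-day carry-forward; the status that decides how the value is scored does not.

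The result is a fall in the score that no observation supports. It can occur only in participants with acute renal failure and raised creatinine, and only in the direction of apparent improvement. It can enter the Day 15 or discharge score used in the primary analysis. If the affected participant were the highest scorer in the trial, it could also lower the value assigned to every death by Day 15, since section 6.1.8 uses the highest observed score for deaths.

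**Working it through.** **Step 1. Check the scoring tables against the plan's own maximum.** Section 6.1.1 gives a range of 0 to 71. From section 10.2.1 and the Glasgow rule in section 10.2:

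- ten physiological items other than creatinine, 10 × 4 = 40
- creatinine with acute renal failure, 8
- age, 6
- chronic health, 5
- Glasgow component, 15 − 3 = 12

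40 + 8 + 6 + 5 + 12 = 71, as stated. With renal status blank the creatinine maximum is 4 and the total can reach only 67.

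**Step 2. Compare the creatinine rows.** Loss = points with acute renal failure − points with a blank.

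| Creatinine (mg/dL) | With acute renal failure | Status blank | Loss | Ratio |
|---|---|---|---|---|
| ≥3.5 | 8 | 4 | 4 | 0.5 |
| 2–3.4 | 6 | 3 | 3 | 0.5 |
| 1.5–1.9 | 4 | 2 | 2 | 0.5 |
| 0.6–1.4 | 0 | 0 | 0 | – |
| <0.6 | 2 | 2 | 0 | 1 |

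For a participant without acute renal failure, or with creatinine below 1.5 mg/dL, a blank changes nothing.

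**Step 3. Follow one participant through the rules.** Section 1.4 schedules in-hospital assessments every 2 days, so a 4-day window back from Day 15 reaches Day 13 (15 − 2) and Day 11 (15 − 4). Suppose Day 13 shows creatinine 3.6 mg/dL with acute renal failure recorded, scoring 8.

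- *Case A.* On Day 15 creatinine is again 3.6 and the status is blank. The item scores 4, a fall of 4 points with no clinical change.
- *Case B.* On Day 15 both are missing. The value 3.6 is carried forward from Day 13. If the status rule is then applied to the blank Day 15 status, the same laboratory result that scored 8 on Day 13 scores 4 on Day 15.

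**Step 4. Effect on means.** Let *f* be the share of an arm affected and *L* the average loss among them (2 to 4 points). The arm mean falls by *f* × *L*. The SAP gives no value for *f*, so the following are assumptions:

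| Assumed *f* | Fall in that arm's mean |
|---|---|
| 1% | 0.02 to 0.04 points |
| 5% | 0.10 to 0.20 points |
| 10% | 0.20 to 0.40 points |

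The summary measure in section 6.1.1 is the difference in means. Ignoring covariate adjustment and any change in the score assigned to deaths, that difference (DFV890 minus control) shifts by −(*f*₁*L*₁ − *f*₀*L*₀), where 1 is the DFV890 arm and 0 is control. With equal *f* and *L* in the two arms the shift is 0. The tabulated figures are reached in the difference only if all affected participants are in one arm. The parts of the SAP that can be read give neither a standard deviation nor a sample size against which to judge these figures.

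**Step 5. Is the status recorded more than once?** The SAP does not say. Two things suggest that it is: section 10.2 ties only age and chronic health points to screening, and section 6.1.6 applies its rules to a given visit.

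**The case against.** The strongest reply is that the rule is an explicit, pre-specified convention. Renal status qualifies the creatinine item and is not one of the 14 scored items. The SAP gives other qualifiers fixed defaults too: section 10.2 applies no temperature correction when no method is selected, and section 10.2.1 scores an unknown pacemaker status as none. This stands. A reader might infer that renal status is the only visit-level input reset to a fixed value, and the document does not support that. What remains is that the clinical measurement itself, creatinine, is carried forward and its status is not.

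A second reply is that *last available assessment* could be read to include the status recorded with a carried-forward creatinine value. That reading is possible, so Case B is at least an ambiguity. Case A does not depend on it.

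Third, carrying a positive status forward is also single imputation and can err the other way, because acute renal failure can resolve. This is true, but the plan already accepts the same risk for creatinine, pH and blood pressure over the same 4 days.

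Fourth, how often the status is collected is not stated, and the supportive analyses in section 6.1.9 are redacted. Both limit what can be claimed, and the second cannot be held against the plan.

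**Conclusion.** The point holds as a low-priority improvement. For a participant with acute renal failure and creatinine of at least 1.5 mg/dL, a blank status removes 2, 3 or 4 points, exactly half the item, even when a positive status was recorded within the previous 4 days. The error can only lower a score.

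Two stronger readings should be resisted. A reader might infer that any blank halves the creatinine points; for participants without renal failure or with lower creatinine it changes nothing. A reader might also infer that the treatment comparison is biased. The document gives no frequency of blanks and no reason to expect one arm to have more, beyond the general fact that the trial is open label. The effect on the treatment difference cannot be derived, is probably small, and largely cancels if blanks are equally common in both arms.

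The conclusion assumes that the status is recorded at more than one visit. If it were not, there would usually be no recent status to carry forward.

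**What to change.** Replace the renal status bullet in section 6.1.6 with wording such as:

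*Missing acute renal failure status is replaced by the last recorded status, carried forward by no more than 4 days. If creatinine is also missing, the carried-forward creatinine value keeps the status recorded with it. Only if no status is available in that window is creatinine scored without renal status.*

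This extends the section's own 4-day rule and keeps the present default as the fallback. It would also bring the status under section 4.2, which lets unscheduled data fill gaps where carry-forward applies. The cost is a short SAP amendment and a small programming change before database lock, with no new data. The downside is that a case of renal failure that resolved within 4 days could keep the doubled points at one visit.

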## 4.2 Unscheduled visits

Data collected at unscheduled visits will be used to replace missing values if a Last observation carried forward (LOCF) approach is applied within the allowed LOCF period of maximum 4 days (i.e. for the mortality scores APACHE II, Commercially Confidential Information as described in [Sections 6.1.6](#) and [Section 6.3.1](#)).

In addition for the screening/baseline visit unscheduled assessments within 24 hours prior to signing the Informed Consent Form (ICF) can be used.

For other type of analyses and other visits no unscheduled visits data will be considered.

Commercially Confidential Information

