**Table 10-1 Conversion of SpO2 to PaO2**

SpO2 (%)	PaO2 (mmHg)
80	44
81	45
82	46
83	47
84	49
85	50
86	52
87	53
88	55
89	57
90	60
91	62
92	65
93	69
94	73
95	79
96	86
97	96
98	112
99	145

6. Arterial pH: if Arterial pH is not available use Serum HCO3 (venous mmol/L) instead
7. Serum Sodium (mmol/L)
8. Serum Potassium (mmol/L)
9. Serum Creatinine (mg/dL=mg/100mL)
10. Hematocrit (%)
11. White Blood Count ( $10^9/L = 1000/mm^3 = 10^3/mm^3$ )
12. Age at Screening (years)
13. Chronic Health Points at Screening:  
Points are assigned only if for this patient “Did the subject experience Severe organ system insufficiency or is immunocompromised ?” is selected as “yes”.
  - If “Did the subject experience Severe organ system insufficiency or is immunocompromised ?” = “no”, no points are assigned and a record should not be created for this question in the SDTM data set.
  - If “Did the subject experience Severe organ system insufficiency or is immunocompromised ?” is selected as “yes” Chronic Health points will be derived from “Admission Classification”:
    - Medical(non-operative)
    - Emergency post-operative
    - Elective post-operative

If in this scenario none of these conditions is selected the Chronic Health points will be set to 0.

14. Glasgow Coma Score: First each sub-score is scored according to the scoring table below

- Best Eye Response
- Motor Response
- Verbal Response

Then these three subscores are added up to obtain the scoring of the “Total Glasgow Coma Score”. The value included in the APACHE II for Glasgow-Coma-Score is then = 15 – “Total Glasgow Coma Score”.

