## 10.5 Glasgow Coma Score

### 10.5.1 Glasgow Coma Scoring

- Best eye response

Result	Score (Char)	Score (Num)
No eye opening	1	1
Eye opening to pain	2	2
Eye opening to verbal command	3	3
Eyes open spontaneously	4	4
Untestable	Untestable	
Unknown	Unknown	

- Motor response

Result	Score (Char)	Score (Num)
No motor response	1	1
Abnormal extension	2	2
Abnormal flexion	3	3
Flexion withdrawal	4	4
Localizes pain	5	5
Obeys command	6	6
Untestable	Untestable	
Unknown	Unknown	

- Verbal response

Result	Score (Char)	Score (Num)
No verbal response	1	1
Incomprehensible sound	2	2
Inappropriate words	3	3

Confused	4	4
Oriented	5	5
Untestable	Untestable	
Unknown	Unknown	

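### The SAP replaces the Glasgow Coma sub-scores of any unconscious participant with the last actual scores, so unsedated coma at Day 15 can be understated by up to 12 APACHE II points

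*SAP*

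**What the plan says.** SAP Section 6.1.6 has one bullet for the Glasgow Coma sub-scores. A sub-score recorded as *untestable*, *unknown* or missing "will be replaced by the last available actual score". The same bullet explains that *untestable* "is selected if the patient is unconscious (e.g. through sedation in case of mechanical ventilation").

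The next bullet covers the remaining items: "Missing values in any of the other parameters required for the derivation of the APACHE II score will be replaced by the last available assessment", and only there does the limit appear: "as long as data is not carried forward by more than 4 days".

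Section 4.2, on unscheduled visits, refers to replacement of missing APACHE II data "within the allowed LOCF period of maximum 4 days" and points back to Section 6.1.6.

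Section 10.5.1 gives each sub-score a lowest category of 1 for no response (for the eyes, "No eye opening"). *Untestable* and *unknown* have no numeric score. Section 10.2, item 14, converts the total into APACHE II points: "The value included in the APACHE II for Glasgow-Coma-Score is then = 15" minus that total. Section 6.1.8 derives the primary combined score after the missing-data rules have been applied.

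**The concern.** The coma item exists to register loss of consciousness. As worded, Section 6.1.6 makes unconsciousness itself the trigger for *untestable* and then treats that entry as missing data. For a sedated, ventilated participant this makes sense, because the drug hides the neurological state and the last score before sedation is a reasonable stand-in. For a participant who loses consciousness from the disease, the state can be observed and has scored categories. Replacing it with an earlier, more awake score gives the wrong value.

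Where the true total is 3, the error has one direction: no carried-forward total can be below 3, so severity is understated or left unchanged. For those alive and in hospital at Day 15, the affected score is the primary outcome. If such participants are more frequent in one arm, the treatment difference moves. If treatment changes how often coma occurs, the endpoint may fail to show it.

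**Working it through.** **Inputs**
- Item formula: 15 minus total Glasgow Coma Score (SAP Section 10.2, item 14).
- Sub-score ranges: eye 1 to 4 ("No eye opening" to "Eyes open spontaneously"), motor 1 to 6, verbal 1 to 5 (Section 10.5.1).
- Replacement rule and absence of a limit for this item: Section 6.1.6.
- Use of the imputed score at Day 15: Section 6.1.8.

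**1. Reproduce the plan's own range.** Section 6.1.1 gives 0 to 71. Summing the item maxima in the SAP's scoring tables: ten physiological items at 4 = 40; creatinine with acute renal failure 8; age 6; chronic health 5; coma item 12. Total 40 + 8 + 6 + 5 + 12 = 71, as stated. So the plan's own range relies on the coma item reaching 12.

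**2. Bounds of the coma item.** Fully awake: 15 − (4 + 6 + 5) = 0. Unresponsive: 15 − (1 + 1 + 1) = 12. As a share of the scale: 12/71 = 16.9%.

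**3. Effect for one participant whose true total at Day 15 is 3 (12 points).**

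| Last actual total | Points carried forward | Understatement |
|---|---|---|
| 15 | 0 | 12 |
| 14 | 1 | 11 |
| 13 | 2 | 10 |
| 11 | 4 | 8 |
| 3 | 12 | 0 |

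Twelve is the maximum. It needs all three last actual sub-scores to be at their highest value.

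**4. Length of carry-forward.** With no limit in the coma bullet, a Day 1 score can supply the Day 15 value, 15 − 1 = 14 days later.

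**5. Effect on the treatment difference.** Let *p* be the share of an arm that is alive, in hospital, unconscious without sedation and coded *untestable* at Day 15, and *u* the average understatement per such participant (*u* ≤ 12), taken as equal in both arms. Each arm mean is understated by *u* × *p*, so the unadjusted difference shifts by *u* × (gap in *p*). The SAP gives no coma rate, so the gaps below are assumptions.

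| Gap between arms | *u* = 12 (upper bound) | *u* = 8 (last total 11) |
|---|---|---|
| 0% | 0 | 0 |
| 2% | 0.24 | 0.16 |
| 5% | 0.60 | 0.40 |
| 10% | 1.20 | 0.80 |

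If the control arm has more such participants, a benefit of DFV890 is understated; if the DFV890 arm has more, it is overstated.

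**The case against.** The strongest defence is that the rule was written for sedated, ventilated patients, the one example it gives, and there it is defensible. Many survivors on mechanical ventilation may fall under that case. Participants who die by Day 15 receive the highest observed score, so their own coma coding does not enter their endpoint. The affected group is thus narrow. That stands and limits the size of the problem, but not the error in the wording: the criterion is unconsciousness, and sedation is introduced only as an example.

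Four stronger readings are tempting, and the document does not support them.
- A reader might infer that sites are obliged to record *untestable* for every unconscious participant, or that they demonstrably differ in doing so. The SAP describes when the response is chosen; the instruction to sites is not shown, so neither can be established.
- A reader might infer that the score misses coma in the sickest survivors generally. That ignores the sedated cases, for which the carry-forward is reasonable.
- A reader might take the shifts above as estimates. They are upper bounds on assumed rates.
- A reader might take Section 4.2 as already capping this item at 4 days. It governs the use of unscheduled-visit data and refers to Section 6.1.6, where the cap covers only the other parameters. The two should be aligned, but the separate coma bullet may be deliberate.

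The supportive analyses in Section 6.1.9 are redacted, so whether one of them addresses this cannot be known.

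**Conclusion.** The point holds for participants alive, in hospital and unconscious without sedation at Day 15. Followed literally, Section 6.1.6 replaces an observable, scorable state with an earlier score and can understate the primary score by up to 12 of 71 points for each of them.

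The wording and the per-participant arithmetic are certain. The effect on the trial result is not: it is bounded by 12 times the between-arm gap, it vanishes if the arms are equally affected, and it assumes the same average understatement in both arms. The absence of a time limit is a separate and lesser matter, an inconsistency of wording between Sections 4.2 and 6.1.6. The change should be made because the rule gives a wrong value in the primary endpoint and is cheap to correct, not because a large bias has been shown.

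**What to change.** In Section 6.1.6:
- Restrict the *untestable* carry-forward to sub-scores that cannot be tested because of sedation, paralysis or intubation. Confirm this from recorded sedatives or paralytics, or from intubation status. A 9-point score of 6 or 7 alone is not enough, since it shows ventilation and not sedation.
- For unconsciousness without these, use the actual Section 10.5.1 category, obtained by query.
- Score any *untestable* entry that remains as 1 in a sensitivity analysis only. In the main analysis this would replace one untested imputation with another that could err in the opposite direction.

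Separately, reconcile the 4-day wording of Section 4.2 with the coma bullet of Section 6.1.6. If a cap is applied to *unknown* or missing sub-scores, state how the resulting missing totals are handled. Section 10.2 makes the total missing before imputation when one item is missing, and no further visible rule would fill it, so a cap could remove Day 15 primary values.

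Cost: SAP wording, one programming check and a few queries.

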#### **7.2.3 Vital signs**

Vital sign measurements include respiratory rate, pulse rate (PR), systolic and diastolic blood pressure, mean arterial pressure body temperature, weight and BMI. Peripheral oxygen saturation on room air or on supplemental oxygen is also measured at the same time as the vitals. In case oxygen saturation is reported for both room air and under supplemental oxygen, the value for room air is included in summary presentations and analysis. For participants requiring supplemental oxygen, the oxygen flow rate (L/min) and/or FiO2 is also recorded.

Summary statistics will be provided by treatment group and visit/time.

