### 2. Mean Arterial Pressure (mmHg)

In case the “method” is reported as “calculated” confirm the calculation by applying the following formula:  $MAP = [SBP + (2x DBP)] / 3$ . If the reported and recalculated numbers differ by more than 10% use the recalculated value (i.e. if reported value < 0.9\* recalculated value or reported value > 1.1\* recalculated value)

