### SDTM Mapping strategy

APACHE II specific mapping strategy: It provides guidance on how the result variables (RSORRES, RSSTRESC, and RSSTRESN) should be populated for the measure. All original results are represented with preferred terminology in RSORRES. This result is then transformed into a standard numeric score in RSSTRESN and a character representation of the standard numeric score in RSSTRESC.

To obtain the total APACHE II score all 14 derived values of RSSTRESN are then added up. If one item is missing the APACHE II score at STDM level for this visit is missing. Missing data imputation will be implemented at ADAM level.

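### A missing mean arterial pressure falls to 4-day carry-forward because no rule derives it from same-visit systolic and diastolic pressure (minor, free to fix)

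*SAP*

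**What the plan says.** **Missing items.** SAP Section 6.1.6 has specific rules for age, acute renal failure status and the Glasgow subscores. For everything else: "Missing values in any of the other parameters required for the derivation of the APACHE II score will be replaced by the last available assessment". The carried value may be at most 4 days old. A precondition applies: the rules operate only at a visit with a recorded value for one or more APACHE II items. Section 4.2 lets unscheduled values fill gaps within the same 4-day window.

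**The MAP item.** Appendix 10.2, item 2 reads: "In case the “method” is reported as “calculated” confirm the calculation by applying the following formula", and then gives MAP = [SBP + (2 x DBP)]/3. It continues: "If the reported and recalculated numbers differ by more than 10% use the recalculated value". Both steps presuppose a reported MAP.

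**What is collected.** Section 7.2.3 lists "systolic and diastolic blood pressure, mean arterial pressure" together among the vital signs.

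**Neighbouring items.** Appendix 10.2 allows PaO2 to be derived from SpO2 when PaO2 is not available at a visit, and uses serum HCO3 when arterial pH is not available.

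**Effect on the total.** The SDTM mapping text in Appendix 10.2 says: "If one item is missing the APACHE II score at STDM level for this visit is missing". It then assigns imputation to the ADaM level. Section 6.1.8 builds the primary variable from scores after that imputation.

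**The concern.** Carry-forward is a reasonable last resort for an item with no other source. MAP has one: two pressures planned for collection with it, and a formula already in the SAP. Item 2 even lets the formula override a reported 'calculated' MAP that disagrees by more than 10%. Yet when MAP is blank, the rule that applies is to take a reading from an earlier time. The SAP gives no reason for treating MAP less favourably than PaO2 or pH, whose substitutes are only surrogates.

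At stake is the accuracy of one of the 14 items in the primary score, at Day 15 or discharge, and in the baseline score that serves as ANCOVA covariate (Section 6.1.3). A carried value is wrong only where blood pressure has moved enough to change the points. A second issue is reproducibility: one programmer may follow Section 6.1.6 literally and another may apply the formula to the blank, and their primary scores would differ.

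**Working it through.** The SAP gives no figure to reproduce. The check has three parts.

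**1. Which rule catches a blank MAP?**
- The confirmation step in item 2 needs a value with method 'calculated'. A blank has none.
- The 10% test replaces a reported value below 0.9 or above 1.1 times the recalculated one. With nothing reported, neither comparison can be met.
- Section 6.1.6 has no MAP-specific line, so the general rule applies: last assessment, at most 4 days old.

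**2. How far can the item be off?** Inputs are the formula in item 2 and the MAP table in Section 10.2.1: 160 or more = 4 points, 130-159 = 3, 110-129 = 2, 70-109 = 0, 50-69 = 2, 49 or less = 4. The pressures and carried values are assumptions, and MAP is rounded to a whole number before scoring.

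| Same-visit SBP/DBP | Derived MAP | Points | Carried MAP | Points | Error |
|---|---|---|---|---|---|
| 120/80 | (120+160)/3 = 93.3 | 0 | 93 | 0 | 0 |
| 120/70 | (120+140)/3 = 86.7 | 0 | 112 | 2 | +2 |
| 120/75 | (120+150)/3 = 90.0 | 0 | 65 | 2 | +2 |
| 85/50 | (85+100)/3 = 61.7 | 2 | 85 | 0 | -2 |
| 150/95 | (150+190)/3 = 113.3 | 2 | 100 | 0 | -2 |
| 65/40 | (65+80)/3 = 48.3 | 4 | 85 | 0 | -4 |

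The error is zero unless MAP crossed a boundary, and it can go either way. The zero-point band covers 70 to 109, so moderate changes within it cost nothing.

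**3. How old is the carried value, and when is the score lost?** Section 1.4 puts assessments every 2 days for hospitalized participants. Counting back from Day 15, and assuming MAP follows that schedule:
- Day 15 blank: Day 13 is used (15 - 13 = 2 days).
- Days 13 and 15 blank: Day 11 is used (15 - 11 = 4 days, still allowed).
- Days 11, 13 and 15 blank: Day 9 is 15 - 9 = 6 days old, beyond the limit. The item and the Day 15 score stay missing unless an unscheduled MAP falls within 4 days.

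**Scale of effect on an arm mean.** The frequency is not given. Suppose 1% to 5% of one arm's primary scores were wrong, all in the same direction. At 2 points each, that arm's mean moves by 0.01 x 2 = 0.02 to 0.05 x 2 = 0.10 points. At 4 points each, it moves by 0.04 to 0.20 points. Errors in both directions, or similar errors in both arms, reduce this further.

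**The case against.** The strongest case on the other side has five parts.

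- **The event may be rare or absent.** MAP has its own entry and a method field with 'calculated' as an option, so sites can enter a value from SBP and DBP. Nothing in the SAP shows that MAP is left blank while both pressures are recorded. This stands; the frequency is unknown.
- **The SAP does not forbid using the formula for a blank.** The PaO2 and pH substitutes also sit in Appendix 10.2, ahead of carry-forward, and a programmer could treat MAP alike. This stands only in part. Section 6.1.6 is a positive rule that covers MAP, and item 2 limits the formula to checking reported values, so the literal reading is carry-forward.
- **The formula is not always exact.** A reader might infer that the plan discards a value known exactly. That holds only for a MAP of method 'calculated'; where MAP would have been measured directly, the formula is an approximation.
- **Participants are not readily lost.** The sentence about a missing item might be read as dropping the participant from the primary analysis. It describes the score before imputation. A lost Day 15 score needs the run of blanks shown above with no unscheduled MAP in the window.
- **Most carried values score the same.** With 2-day visits and a wide zero-point band, this stands.

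Baseline differs a little. There is generally no earlier scheduled visit to carry from, and Section 4.2 adds only unscheduled assessments within 24 hours before consent. However, Table 4-1 treats a screening APACHE II score below 10 as a deviation, which suggests that a score was worked out at entry and makes a blank baseline MAP less likely.

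**Conclusion.** The point holds as a minor gap in the derivation of the primary score. Read literally, the SAP sends a blank MAP to the 4-day carry-forward rule, and no rule derives it from same-visit SBP and DBP. An affected item is typically off by 2 points, by 4 in extreme cases, and only when MAP crossed a scoring boundary since the last reading. The visit score stays missing only if no scheduled or unscheduled MAP lies within 4 days.

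The document does not support any claim of material bias in the treatment comparison. The frequency is not given, no direction between arms follows from the text, and even the one-sided illustration above moves an arm mean by at most 0.20 points. That range rests on an assumed 1% to 5% of scores affected. The reason to act is that the change is free, agrees with the SAP's own practice for PaO2 and pH, and removes a choice otherwise left to the programmer.

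**What to change.** Add one sentence to Appendix 10.2, item 2, and refer to it in Section 6.1.6: if MAP is not recorded at a visit but SBP and DBP are, MAP is derived from them as [SBP + 2 x DBP]/3; carry-forward applies only if MAP cannot be derived. State that this also applies at baseline, and that the derived value is an approximation where MAP would have been measured directly. A count by treatment group of visits with derived MAP would show how often the rule was used.

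The cost is one sentence in the SAP and one line of programming. It needs no new data and leaves the model and the scoring table as they are.
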